6.3.1. Stopping Rules in an Individual Subject or in a Cohort

For this clinical trial a treatment period is defined as period of time from the beginning of dosing of the first study drug on a given dosing day (ie, Either saline placebo or SEL-110 during Part A of the study and SEL-037 during Part B of the study) to the beginning of the next scheduled dose of study drug, and has a typical duration of 28 days.

For Part C (Cohorts 13, 15, and 17), a treatment period is defined as the period of time from the beginning of dosing of SEL-212 to the beginning of the next scheduled dose of study drug.

Individual

For subjects in Cohorts 1 and 2, any subject who has a weekly serum uric acid value ≥ 6 mg/dl or $>50\%$ of their baseline (where baseline value refers to the pre-dose serum uric acid level from visit 4, Day 0, treatment period 1) at Day 21 of their current treatment cycle will not be eligible for the next dosing of SEL-037. The subject will be followed for 30 days post the last dose of study drug at which time they will have an End of Study assessment and their participation in the study will be terminated.

In Cohorts 3-8, 10-13, 15, and 17 only subjects whose ambient blood samples indicate a serum uric acid (sUA) value less than or equal to 1.0 mg/dL at any of the Day 21 visits will be eligible for the next dosing of SEL-212 (or SEL-037). All other subjects will be followed for 30 ± 2 days post the last dose of study drug at which time all of the End of Study assessments will be completed and their participation in the study will be terminated.

Cohort

If 5 subjects in any of Cohorts 1-5 or 7, or if 10 subjects in any of Cohorts 6, 8, 10, 11, or 12 have met the requirements for individual stopping of their participation in the trial as described above or have been stopped based on Section 6.4 then that cohort will no longer have any additional subjects enrolled in it. Those subjects who have been enrolled will continue until they fulfill the requirements

Study: SEL-212/201 Version: 7.1	Effective Date March 19, 2018
------------------------------------	----------------------------------

for individual stopping or complete the clinical trial treatment periods. If they continue to meet the requirements for continued participation they may continue in Part B of the study.

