8.2. PHARMACOKINETIC PARAMETERS

The following PK parameters will be calculated on SEL-037 and SEL-110 (rapamycin) PK concentration as well as uricase activity using noncompartmental intravascular infusion log-linear model for each Cohort and Treatment Period where possible and summarized statistically:

C_{max}	Maximum observed PK concentration or activity
T_{max}	Time of maximum observed PK concentration or activity
C_{last}	Last observed PK concentration or activity
T_{last}	Time of last observed PK concentration or activity
AUC_{0-last}	Area under the serum concentration-time curve from time zero to the time of the last quantifiable PK concentration or activity
AUC_{0-inf}	Area under the PK concentration or activity-time curve from time zero extrapolated to infinity
$t_{1/2}$	Terminal elimination half-life
λ_z	Terminal elimination rate constant
CL	Clearance of drug
V_d	Terminal volume of distribution

Statistical Analysis Plan

Additional PK parameters may be calculated as needed.

Multiple dose parameters will be also derived where possible:

C_{min}	Min observed trough PK concentration or activity
T_{min}	Time of min observed PK concentration or activity
C_{ave}	Average observed PK concentration or activity
AUC_{tau}	Area under the PK concentration or activity from time 0 to the end of dosing interval
% Fluctuation	Difference between C_{max} and C_{min} normalized by average concentration
R_{AUCtau}	Accumulation ratio based on comparison of AUC_{tau} between last and first dose
R_{Cmax}	Accumulation ratio based on comparison of C_{max} between last and first dose
R_{Cmin}	Accumulation ratio based on comparison of C_{min} between last and first dose
CL_{ss}	Steady state clearance (if steady state is achieved)

Dose dependent parameters for SEL-110 (C_{max} , AUC_{0-last} , AUC_{0-inf}) will be dose normalized for comparison between treatments involving different doses of SEL-037.

The PK parameters will be estimated as follows:

The apparent C_{max} and the corresponding T_{max} will be read directly from the concentration-time plot (observed data, not predicted data by the program);

AUCs will be calculated using the linear-log trapezoidal rule;

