The terminal elimination rate constant (λ_z) will be determined by log linear regression obtained on at least the 3 last quantifiable concentrations and will not include C_{max} . The adjusted square of the correlation coefficient (Rsquare adjusted) for the goodness of fit of the regression line through the data points must be at least 0.8500 for the λ_z value to be considered reliable;

$t_{1/2}$ is calculated by the program as $\ln 2 / \lambda_z$;

If the time interval between the lower and upper time points used for the regression spans less than the derived half-life itself then λ_z and the associated $t_{1/2}$ will be considered unreliable;

The AUC from 0 to infinity is calculated by the program as:

$AUC_{inf} = AUC_{last} + AUC_{last-inf}$ where last is the sampling time point of the last measurable concentration (t_{last}). $AUC_{last-inf}$ is calculated by the program as: C_{last} / λ_z , where C_{last} is the

Statistical Analysis Plan

observed concentration at time t_{last} and λ_z is the elimination rate constant during the apparent terminal elimination phase; AUC_{inf} will only be presented for subjects with a reliable λ_z ;

The AUC extrapolation to infinity must be $\leq 20\%$ of the total area for AUC_{inf} to be considered reliable;

CL is calculated by program as $(dose/AUC_{inf})$

V_d is calculated by the program as $(dose/AUC_{inf})/\lambda_z$.

For subjects with unreliable λ_z (ie, Rsquare adjusted < 0.8500 , interval for λ_z calculation shorter than $t_{1/2}$, number of points to calculate $\lambda_z < 3$), λ_z , $t_{1/2}$, AUC_{inf} , CL and V_d will be flagged in the individual data.

For subjects with unreliable AUC_{inf} (because of extrapolation $> 20\%$), AUC_{inf} , CL and V_d will be flagged in the individual data.

Flagged PK parameters will be excluded from summarization and statistical analyses.

8.2.1. Handling of Dropouts, Missing Data or Data Below the Lower Limit of Quantification

Missing concentration data for all subjects who are administered scheduled study treatments will be considered as non-informative missing and will not be imputed for each treatment period individually. The missing data will not affect analyses for the previous treatment periods where complete dose were administered and PK profiles available. No concentration estimates will be provided for missing sample values.

For the derivation of PK parameters, the following rules will apply:

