Concentration values below the assay's lower limit of quantification (BLQ) in pre-dose samples and in samples taken before the time of the first quantifiable concentration will be treated as zero.

The sampling time of pre-dose samples relative to dosing will also be treated as zero.

Post-dose BLQ values after the first quantifiable time point will be set to missing.

If the actual time of sampling is missing, the planned time may be used.

Statistical Analysis Plan

Samples taken outside the sampling windows may be excluded from by-time point summary statistics. This will be determined prior start of analyses around timing for database lock.

For serum or whole blood concentration summary, individual concentration versus time curves and mean concentration versus time graphs, the following rules will apply:

- Serum or whole blood concentrations BLQ in pre-dose samples and in samples taken before the time of the first quantifiable value will be set to zero
- The serum or whole blood concentrations BLQ after quantifiable concentration will be set to zero

No further imputation will be applied to any missing values.

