The CL for SEL-037 (pegsiticase), C_{max} , T_{max} , AUC_{0-last} , and AUC_{0-inf} derived using both PK concentrations and uricase activity will be compared between subjects with cumulative negative and cumulative positive ADA results by Treatment period and cohort and overall for each cohort individually in the descriptive statistics table.

Similarly, PD parameters C_{min} , CFB_{min} , $AUE_{CFBlast}$, $TA_AUE_{CFBlast}$, $\%CFB_{min}$, $AUE_{\%CFBlast}$ and $TA_AUE_{\%CFBlast}$ will be compared between subjects with cumulative negative and cumulative positive ADA results by Treatment period and cohort and overall for each cohort individually in the descriptive statistics table.

No statistical inferences will be done for the comparisons.

Statistical Analysis Plan

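### SAP 8.2 computes SEL-037 clearance as dose/AUCinf after every dose without removing drug left from earlier doses, so CL and Vd are understated from Period 2 wherever a residual is measurable

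*SAP*

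**What the plan says.** SAP 8.2 derives the PK parameters for SEL-037 concentration, uricase activity and SEL-110 by a non-compartmental "intravascular infusion log-linear model for each Cohort and Treatment Period where possible and summarized statistically". Within that section "CL is calculated by program as" dose/AUCinf, and Vd is the same ratio divided by lambda-z. AUCinf is AUClast plus Clast/lambda-z from the profile of that period. No restriction to the first dose is stated.

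BLQ values "in pre-dose samples and in samples taken before the time of the first quantifiable concentration will be treated as zero" (SAP 8.2.1). A quantifiable pre-dose value stays in the profile, and no residual subtraction is described for it. SAP 4.1 allows change from baseline as an option for uricase activity, but SAP 6.2 fixes baseline before the first infusion of Period 1, so this does not remove later residuals.

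Three provisions bear on the point:
- "The AUC extrapolation to infinity must be" at most 20% of the total area. Otherwise AUCinf, CL and Vd are flagged and left out of summaries and analyses.
- AUCtau is derived, and a further parameter is listed as "Steady state clearance (if steady state is achieved"), with no formula and no test of steady state.
- The antibody comparison in SAP 10.5 begins "The CL for SEL-037 (pegsiticase"), and the box plots in SAP 10.4 also use CL. Neither uses the steady-state parameter. The comparison is made by period, by cohort and overall, and is descriptive.

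**The concern.** Dose/AUCinf equals clearance only if the whole area comes from the dose in the numerator. After a second or later dose, the area also contains what earlier doses left behind, while the numerator holds only the current dose. The ratio can then err only downward.

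The documents make carry-over of SEL-037 likely. Entry requires serum uric acid of at least 6 mg/dL (Protocol 7.1). In Cohorts 3 and above, the next dose is given only if the Day 21 value is at or below 1.0 mg/dL (Protocol 6.3.1). SAP 5.4 states that only SEL-037 lowers uric acid. Protocol 10.1.1 reports an effect lasting beyond 30 days in 17 of 31 subjects, longer than the dosing interval.

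The bias is also uneven. Protocol 4.3.2.1 says that ADA generally went with faster SEL-037 clearance. Residual drug, and so the understatement, should be larger in slow clearers, who tend to be ADA-negative. That would widen the CL difference by antibody status and add a spurious drop in CL from Period 1 to Period 2. SEL-037 PK and immunogenicity are secondary objectives. AUCinf appears in the same antibody tables and contains the same carry-over.

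**Working it through.** The plan states no SEL-037 clearance, half-life or accumulation figure, so there is nothing to reproduce first. The check uses linear superposition.

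**Inputs**
- CL = dose/AUCinf, in every period (SAP 8.2).
- Dosing interval: a treatment period "has a typical duration of 28 days" (Protocol 6.3.1), that is 672 h.
- Last sample: Day 28 pre-dose (672 h), or Day 30 (720 h) in Period 5 (SAP 8.1).
- Assumption: SEL-037 half-life of 3 to 12 days, one compartment, true CL constant over periods.

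**Formula**

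Let r = exp(-lambda-z × 672 h) = 2^(-28/half-life in days), the fraction left after one interval. In Period n the area to infinity is (dose/CL) × (1 + r + … + r^(n-1)), so

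apparent CL / true CL = (1 - r)/(1 - r^n).

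In Period 2 this is 1/(1 + r). At 7 days, for example, r = 2^(-4) = 0.0625 and 1/1.0625 = 0.941.

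| Half-life (days) | r | Period 1 | Period 2 | Period 3 | Period 5 |
|---|---|---|---|---|---|
| 3 | 0.0016 | 1.000 | 0.998 | 0.998 | 0.998 |
| 5 | 0.0206 | 1.000 | 0.980 | 0.979 | 0.979 |
| 7 | 0.0625 | 1.000 | 0.941 | 0.938 | 0.938 |
| 10 | 0.1436 | 1.000 | 0.874 | 0.859 | 0.856 |
| 12 | 0.1984 | 1.000 | 0.834 | 0.808 | 0.802 |

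Simulating the SAP's rules (1 h infusion, uricase-activity sampling times, linear-log trapezoid, lambda-z from the last three points) agreed to within 0.001. Vd carries the same proportional error.

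**Cap from the 20% rule**

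In this model the extrapolated share is exp(-lambda-z × tlast). Requiring it to be at most 0.20 gives half-life ≤ tlast × ln2/ln5:
- tlast 672 h: 289 h (12.1 days); r at most 0.20; understatement at most about 20%.
- tlast 504 h (Day 21): 217 h; r at most 0.117; at most 11.7%.
- tlast 720 h (Period 5, Day 30): 310 h; r at most 0.223; at most about 22.3%.

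**Antibody contrast, illustrative**

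Take half-lives of 3 days (ADA-positive) and 10 days (ADA-negative) with equal volume. The true CL ratio is 10/3 = 3.33. The SAP formula gives 3.33 × 1.1436/1.0016 = 3.81 in Period 2, and 3.89 in Period 5. The ratio is inflated by about 14% to 17%.

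**Check of the remedies**
- Dose/(AUCinf - Cpredose/lambda-z) returned 1.000 of true CL in Periods 1 to 5 at all half-lives from 3 to 12 days.
- Dose/AUCtau equals true CL × 1/(1 - r^n). At half-lives up to 12 days it is at most 1.041 in Period 2 and 1.008 from Period 3. In Period 1 it overstates CL: 1.07 at 7 days and 1.25 at 12.

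**The case against.** The strongest reply is that the size is unknown and may be trivial. No SEL-037 half-life is given, and at 5 days or less the error is about 2% or smaller. Suppressed uric acid shows that some enzyme is active, not how much remains. In the single-dose study (Protocol 4.3.2.1) uric acid was below quantification from Study Day 2 at every dose down to 0.1 mg/kg, and duration appeared to depend on the subject rather than the dose. This stands, and it is why the size can only be given as a range.

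Little also rests on CL. The antibody comparison is descriptive, Period 1 CL is unbiased and is shown separately, and the models in SAP 8.5-8.7 name AUC, Cmax and Cmin rather than CL. In the illustration a ratio of 3.33 becomes 3.81 to 3.89, so the qualitative message survives. This stands too, and it limits the consequence. It does not make the later-period values correct.

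The planned steady-state clearance is a partial answer. Without a formula or criterion, and unused in SAP 10.4-10.5, it does not repair the CL that is reported there.

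A reader might infer that the bias falls only on antibody-free subjects and is absent in ADA-positive ones. The documents do not support that. Re-dosing is decided on Day 21 uric acid, Cohorts 1 and 2 use a different uric acid rule, and SAP 10.4 plans to tabulate ADA-positive and ADA-negative subjects within each uric acid group. An ADA-positive subject who is re-dosed can have carry-over as well. A reader might also extend the table to longer half-lives. At 14 days the formula gives 20% in Period 2 and 25% in Period 5, but the extrapolated share is then 25% with a Day 28 last sample and 22.6% with Day 30. The SAP would exclude those values.

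**Conclusion.** As written, SAP 8.2 gives SEL-037 CL and Vd values that are too low from Period 2 on wherever a quantifiable residual precedes the dose. The direction follows from the formula and needs no half-life. The size does: from under 1% at 3 days to 17% (Period 2) and 20% (Period 5) at 12 days, with the cap shown above. These figures assume one compartment, a 28-day interval, linear kinetics and clearance that does not change between periods.

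Most of the error appears as a single step between Periods 1 and 2, with little further change. It can exaggerate the CL difference by antibody status but would not by itself create one of the size illustrated. The primary safety objective is unaffected. The point is worth correcting because the rule is biased as stated and the correction uses quantities already planned.

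**What to change.** In SAP 8.2:
- Report CL = dose/AUCinf for Period 1 only.
- For Periods 2-5, define CL as dose/(AUCinf - Cpredose/lambda-z), and state the assumption that the residual declines at the current period's lambda-z. This needs saying because antibodies may change clearance. Alternatively, use dose/AUCtau as the steady-state clearance, with its formula and a stated steady-state criterion.
- Derive Vd from the same clearance.

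In SAP 10.4-10.5, use the same quantity in the tables and box plots, and base the main comparison of CL by antibody status on Period 1 or on the corrected values. SAP 8.2 applies one formula to both drugs, so the wording should cover SEL-110 too.

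The cost is SAP text and a small change to the derivation. The Day 28 pre-dose sample is already scheduled in SAP 8.1, and lambda-z and AUCtau are already derived.

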8.3. DATA SUMMARIZATION

PK parameters and serum (SEL-037) or whole blood (SEL-110) concentration data will be summarized by treatment using the following descriptive statistics:

Variable	Summarized with:
Serum or whole blood concentration at each nominal time point	n, number and % BLQ, arithmetic mean, SD, coefficient of variance (CV) %, minimum, median and maximum
AUC, C _{max} , CL and V _d	n, arithmetic mean, SD, CV%, minimum, median, maximum, geometric mean and geometric CV%
t _{1/2} , and λ _z	n, arithmetic mean, SD, CV%, minimum, median, maximum
T _{max} (actual time)	n, minimum, Q1, median, Q3 and maximum

Note: CV% = SD/mean in %.

%BLQ = 100 * (total number of subjects who have BLQ values/total number of subjects within each cohort at each time point)

Mean concentrations will not be presented if 30% or more of the actual values for PK analysis set at any one time point in the terminal phase are BLQ or missing.

Samples taken outside the allowed time windows may be excluded from summarization. This will be determined prior to database lock.

The following conventions will be used for the presentation of the descriptive statistics of PK parameters and of serum or whole blood concentrations:

Statistical Analysis Plan

PK Reporting Precision

Statistics	Degree of Precision
Minimum, Maximum	3 significant digits or as needed based on actual measured values (for example PK concentrations)
Mean (arithmetic and geometric), Median	4 significant digits or as needed based on actual measured values (for example PK concentrations)
Standard deviation	5 significant digits or as needed based on actual measured values (for example PK concentrations)
CV% and Geometric CV%	1 decimal point or as needed based on actual measured values (for example PK concentrations)

8.4. DATA PRESENTATION FOR SEL-110 AND SEL-037

The actual sampling time of PK blood sample collection will be listed for each cohort and will include the deviation in time from the protocol scheduled time, if applicable.

Individual subject serum (SEL-037) or whole blood (SEL-110) concentration data will be listed by subject, time point and treatment (in relevant concentration units) and will be summarized at each time point by cohort. Individual subject PK parameters will be listed for the PK analysis set in a table by subject and will be summarized, by treatment group/cohort. Unreliable PK parameters will be listed but flagged and excluded from the summary.

PK parameters of secondary interest, namely Rsquare adjusted, the number of data points used for estimating λ_z , the upper and lower time point used for estimation of λ_z , and the % AUC extrapolation from t_{last} to infinity will be listed by subject and dose level/cohort to enable verification of the exclusions, if any, of data from the summary statistics of the PK parameters of primary interest.

The following figures will be produced for SEL-110:

Mean \pm SD whole blood concentration-time profiles will be presented, combining the curves for all treatment periods within the same figure for each cohort separately. Individual whole blood concentration-time profiles will be presented, for each cohort with all subjects in the same figure on linear and log-linear scales - 3 curves on the plot

Statistical Analysis Plan

for 3 treatment periods for Part A (cohorts 1-8, 10-12, treatment periods 1-3). For Part C of the study (cohorts 13, 15) the presentation will include 5 curves for treatment periods 1-5 on the same plot.

Additional mean \pm SD whole blood concentration-time profiles will be presented, combining the curves for all dose levels of SEL-110 separately in Part A for cohorts with 0.2 mg/kg SEL-037 (cohorts 3, 5, 7, 11) and 0.4 mg/kg SEL-037 (cohorts, 4, 6, 8, 10, 12) within the same figure for each of the three treatment periods 1-3 on a separate plot - 4 and 5 curves respectively, 6 plots total for 3 treatment periods.

The following figures will be produced for SEL-037:

Mean \pm SD serum concentration-time profiles will be presented on linear and log-linear scales for all Treatment periods within the same figure for each cohort separately. PK concentrations of SEL-037 and uricase activity will be also presented on the same plot with double Y axes for each Cohort and Treatment period separately.

Additionally mean \pm SD serum concentration-time profiles will be presented on linear and log-linear scales for all cohorts in Parts A/B with 0.2 mg/kg SEL-037 (cohorts 1, 3, 5, 7, 11) or 0.4 mg/kg dose levels (cohorts 2, 4, 6, 8, 10, 12) within the same figure for each treatment period separately. Cohorts 13, 15 in Part C of the study will be presented separately.

Individual serum concentration-time profiles will be presented, for each Cohort and Treatment period with all subjects in the same figure on linear and log-linear scales.

Regression/scatter plots for SEL-037 PK parameters (C_{max} , AUC_{0-last} , AUC_{0-inf}) for dose levels 0.2 and 0.4 mg/kg separately versus dose of SEL-110 (for cohorts 1 and 2, the SEL-110 dose level will be set to 0) on the same plot for each parameter individually. The plots will be produced for all treatment periods in Part A of the study separately and can be combined for treatment periods 1-3 with Part C data cohorts 13, 15 as additional plot.

8.5. ASSESSMENT OF DOSE PROPORTIONALITY FOR SEL-110

Exploratory dose proportionality will be analyzed with the method originally described by Gough et al. (1995)¹ and modified as described by Smith et al. (2000)² and further adapted by Hummel et al. (2009)³. Hereby Analyses of Variance model (ANOVA) method will be performed on the logarithm e transformed PK parameter endpoints: C_{max} , AUC_{0-last} and AUC_{0-inf} , C_{min} and AUC_{tau} for all treatment periods 1-3 in Part A of the study. Additional analysis may combine Part A data with the data from Part C treatment periods 1-3. The model will include log e-transformed SEL-110 dose level as independent variable. This model will be used to investigate the null hypothesis (H_0):

Statistical Analysis Plan

$\beta=1$). Dose-proportionality will be rejected if the 90% confidence interval (CI) of the estimated slope falls outside the critical interval. The linear form of the model will be as following:

$$Y_{ij} = \alpha + \beta * X_i + \epsilon_{ij}$$

Where:

- Y_{ij} = logarithm of the pharmacokinetic endpoint for subject j at dose level i ; where $i = 1, 2, \dots, m$, $j = 1, 2, \dots, n$
- α = intercept parameter
- β = slope parameter
- X_i = logarithm of dose i
- ϵ_{ij} = random error associated with subject j at dose level i (assumed to be independent and identically normally distributed).

An example SAS code will be:

```
PROC MIXED DATA=xx ALPHA = .1;  
MODEL loge(PK parameter) = loge(dose of SEL-110) / CL;  
RUN;
```

The critical interval will be calculated as follows: First the ratio (r) of the highest dose level to the lowest dose level will be calculated. The lower limit of the critical interval will be calculated as: $\text{Ln}(0.5)/\text{Ln}(r) + 1$. The upper limit of the critical interval will be calculated as: $\text{Ln}(2.0)/\text{Ln}(r) + 1$.

r value is based on the ratio between highest and lower dose levels of SEL-110 and equals to $0.15 / 0.05 \text{ mg/kg} = 3$

Thus critical interval to declare dose linearity will be 0.37 to 1.63 for 90% confidence interval of the slope estimate.

The effect of SEL-037 doses may be explored by including them as fixed covariate effect in the model. p -value for SEL-037 dose will be presented.

Additionally PK parameters C_{\max} , $AUC_{0\text{-last}}$ and $AUC_{0\text{-inf}}$, C_{\min} , AUC_{τ} with total dose and body weight adjusted dose will be investigated using Pearson correlation analysis to estimate which type of dosing has an effect on pharmacokinetics of SEL-110. The correlations for combination with 0.2 and 0.4 mg/kg SEL-037 will be explored separately and overall. The data for Parts A and C (treatment periods 1-3 only) will also be combined in the separate table.

Statistical Analysis Plan

The FISHER option in the PROC CORR statement will be used to estimate confidence limits and p-values for Pearson correlation coefficients based on Fisher's z transformation. Alpha value and a null hypothesis value will be specified for 95% two-sided confidence interval.

Dose proportionality analysis for both Hummel power analysis and Pearson correlation analysis will be also presented graphically as described in [Section 8.4](#) of the SAP. Dose proportionality plots will be presented for SEL-110 C_{max} and AUC_{0-inf} and AUC_{0-last} for Part A only and for combined data from Parts A and C treatment periods 1-3.

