12.5. Pharmacodynamic Analyses

Pharmacodynamic analysis will be as described in the Statistical Analysis Plan.

Data will be listed for all individual subjects with available uric acid serum concentrations. For each dose, descriptive statistics, including arithmetic mean, standard deviation, and geometric mean, coefficient of variation, median, minimum, and maximum will be calculated at each sampling time.

The relationship of PK and PD will be explored and may be analyzed by Spearman rank-order correlations between serum uricase concentration and serum uric acid concentrations by each time point and overall time points. The corresponding p-values will also be provided.

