8.7. ASSESSMENT OF EFFECT OF VARIOUS DOSES OF SEL-110 ON PHARMACOKINETICS OF SEL-037

Effect of co-administration of various doses of SEL-110 on pharmacokinetics of SEL-037 PK parameters for serum concentrations or uricase activity for cohorts 1, 3, 5, 7, 11 (SEL-037 dose 0.2 mg/kg) and 2, 4, 6, 8, 10, 12 (SEL-037 dose 0.4 mg/kg) separately (SEL-110 dose in cohorts 1 and 2 will be set to 0) will be performed by a linear mixed-effect model:

$$PKparam(SEL - 037) = \alpha + s_i + \beta \times Dose(SEL - 110) + e_i$$

α : population mean intercept

β : population mean slope

s_i : random effect of subject i on the intercept, iid $N(0, \sigma_s^2)$

e_i : residual, iid $N(0, \sigma_e)$ for subject i

Statistical Analysis Plan

the PK parameters and dose of SEL-110 will not be log-transformed to allow inclusion of 0 dose of SEL-110 into the model

P value will be calculated for slope and intercept. If the p-value of the slope is less than 0.05, a direct relationship is declared. If p value for slope will be >0.05 the result will be interpreted as lack of effect of SEL-110 on pharmacokinetics of SEL-037.

SEL-110 co-administration effect will also be explored graphically with scatter plots of C_{max} , AUC_{0-last} and AUC_{0-inf} for SEL-037 serum concentrations or uricase activity vs dose levels of co-administered SEL-110 including 0 dose for placebo.

The example SAS code will be:

```
PROC MIXED DATA=data_set_name;  
CLASS treatment;  
MODEL PK Parameter = dose /DDFM=KR;  
LSMEANS dose / CL;  
RUN;
```

Additionally the effect of SEL-110 on PK of SEL-037 will be performed by comparison of data from Parts B vs Part C for treatment periods 4-5 using ANOVA model as described in the Section 8.6 of the SAP.

The contrasts will include:

- Cohort 13 treatment period 4 vs Cohort 11 treatment period 4
- Cohort 13 treatment period 5 vs Cohort 11 treatment period 5
- Cohort 15 treatment period 4 vs Cohort 11 treatment period 4
- Cohort 15 treatment period 5 vs Cohort 11 treatment period 5
- Cohort 15 treatment period 4 vs Cohort 13 treatment period 4
- Cohort 15 treatment period 5 vs Cohort 13 treatment period 5

Graphic presentation in the form of box plots will be also added to the exploratory analysis.

Statistical Analysis Plan

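### On its natural reading SAP 8.5 stacks Periods 1-3 with independent errors; the 8.7 code drops its own subject effect, and Protocol 12.5 attaches p-values to pooled serial samples

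*SAP*

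**What the plan says.** **SAP 8.5.** The exploratory power model regresses log SEL-110 exposure parameters on log dose "for all treatment periods 1-3 in Part A of the study". Its subscripts are subject and dose level, with no period index, and its errors are "assumed to be independent and identically normally distributed". The example code is PROC MIXED with "MODEL loge(PK parameter) = loge(dose of SEL-110) / CL" and no RANDOM, REPEATED, BY or period term. The decision rule reads: "Thus critical interval to declare dose linearity will be 0.37 to 1.63 for 90% confidence interval of the slope estimate". SEL-037 dose may be added as a covariate with a p-value, and Part C Periods 1-3 may be added to the data. The same section plans Pearson correlations with Fisher-z limits and p-values, and adds: "The data for Parts A and C (treatment periods 1-3 only) will also be combined in the separate table".

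**SAP 8.7.** The equation for SEL-037 parameters against SEL-110 dose has a random subject intercept and a residual. The example code names only treatment in CLASS, has no RANDOM statement, and then requests "LSMEANS dose / CL". A slope p-value below 0.05 is to be read as a relationship, and one above 0.05 as no effect.

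**Protocol 12.5.** An optional Spearman analysis relates "serum uricase concentration and serum uric acid concentrations by each time point and overall time points", with p-values.

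**SAP 9.7.** Spearman correlations and a PROC GLM regression relate derived PK and PD parameters. Neither states whether a row is a subject or a subject-period. The PD treatment model in the same section does carry a random subject term.

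**The concern.** A subject in Part A of a SEL-212 cohort can supply up to three periods of PK parameters, all at one assigned SEL-110 dose per kg. Dose then varies only between subjects, so three rows from one subject tell less about the slope than rows from three subjects. A model with independent errors ignores this and, if records within a subject are positively correlated, understates the standard error.

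Stacking is the natural reading of 8.5 because the SAP marks separation where it wants it. Section 8.4 asks for the SEL-037 parameter plots by Part A period, separately, and 8.6 runs its ANOVA separately by part and period. Section 8.5 uses almost the 8.4 phrase without that word.

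At stake are the reported slope interval, the SEL-037 covariate p-value, the Fisher limits, the significance rule in 8.7 and any p-value on a pooled correlation.

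**Working it through.** **The plan's own figure.** The dose ratio is r = 0.15/0.05 = 3. The limits are 1 + ln(0.5)/ln(3) = 0.369 and 1 + ln(2)/ln(3) = 1.631. This reproduces 0.37 to 1.63.

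**Inputs.** Rows per subject if stacked: m = 3 (SAP 8.5). Interval level 90% (8.5); test level 0.05 (8.7). Within-subject correlation ρ: not given in either document, so 0.3 to 0.9 is an assumption.

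**Stacked model, no loss between periods.** With dose constant within subject:

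- design effect DE = 1 + (m − 1)ρ
- standard error understated by √DE
- true coverage of a nominal 90% interval = 2Φ(1.645/√DE) − 1
- true size of a nominal 5% test = 2(1 − Φ(1.96/√DE))

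| ρ | DE | √DE | Coverage | Size |
|---|---|---|---|---|
| 0.3 | 1.6 | 1.265 | 0.807 | 0.121 |
| 0.5 | 2.0 | 1.414 | 0.755 | 0.166 |
| 0.7 | 2.4 | 1.549 | 0.712 | 0.206 |
| 0.9 | 2.8 | 1.673 | 0.674 | 0.241 |

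The same sizes apply to the 8.7 slope test if its rows are stacked and the code is run without a subject term.

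**Simulation check.** Nine SEL-212 cohorts of nine subjects (81 in all), log-scale SD 0.3 and 3,000 trials per setting, all assumed. With no loss, pooled coverage was 0.802, 0.750, 0.719 and 0.673 for the four values of ρ, in line with the table. The Day 21 uric acid rule (Protocol 6.3.1) removes subjects between periods. With 30% or 50% random loss per period, coverage was 0.711 to 0.845 and size 0.089 to 0.206. One row per subject (the subject mean) restored coverage to about 0.90. With no loss, mean interval width rose from 0.16 to between 0.21 and 0.27.

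**Effect on the proportionality verdict.** At a true slope of 1, log SD 0.2 to 0.5 and 54 to 81 subjects, both the pooled and the subject-level 90% intervals lay inside 0.37-1.63 in at least 98% of simulations. The least favourable setting (54 subjects, SD 0.5, ρ 0.7) gave 0.998 pooled and 0.983 by subject.

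**Correlations.** Two unrelated variables, each with within-subject correlation ρ, 80 subjects, Spearman at 0.05. Variance inflation is roughly 1 + (rows − 1)ρ².

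| Rows per subject | ρ = 0.3 | ρ = 0.5 | ρ = 0.7 |
|---|---|---|---|
| 3 (periods) | 0.078 | 0.107 | 0.161 |
| 10 (time points) | 0.135 | 0.257 | 0.391 |

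One row per subject gave 0.048. Ten rows is about one period of sampling: SAP 9.2 lists ten uric acid times from pre-dose to Day 21 for Cohorts 1-2 in Periods 1-3.

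**SAP 8.7, equation against code.** A subject intercept and a residual can be separated only with several rows per subject, so the equation presupposes repeated records. The code fits neither that intercept nor anything equivalent. The least-squares-means line is a separate fault: it needs a CLASS effect, and dose is a continuous regressor there. It narrows no interval, but the line cannot run as written.

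**The case against.** The strongest reply is that 8.5 never says the periods are stacked. Its subscripts allow one record per subject at a dose, for which independent errors are correct. PK parameters are derived by cohort and period (SAP 8.2), and the all-dose SEL-110 plots in 8.4 are one per period. This stands as far as it goes: pooling is inferred, and if each period is fitted alone the stated 90% and 5% levels hold. The remaining defect would be that the text does not say so.

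The written model in 8.7 already contains the subject term, and the code is labelled an example. That also stands; the fault there is a mismatch, and the inflated size arises only if the code is followed on stacked rows.

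Protocol 12.5 is optional, also plans valid correlations at each time point, and defers PD analysis to the SAP, whose correlations use derived parameters. So the ten-row figures apply only to the protocol's all-time-points option. For SAP 9.7, stacked by period, the three-row figures are the relevant ones.

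A reader might infer that all the PK dose models are affected, or that the dose-proportionality conclusion cannot be trusted. The documents do not support either. SAP 8.6 runs by period, the 9.7 PD model has a subject term, and the simulated verdict hardly moves.

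**Conclusion.** The point holds in limited form. On its natural reading 8.5 gives a slope interval that is too narrow and a SEL-037 covariate p-value that is too small. The 8.7 code does not fit the 8.7 equation. An all-time-points Spearman p-value is invalid as a test across subjects.

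The size is 67-81% coverage for a nominal 90% interval (71-85% with 30-50% loss per period), and 0.12-0.24 true size for a 5% test (0.09-0.21 with that loss). For correlations pooled over ten time points it is about 13-39% false positives at ρ of 0.3 to 0.7. These figures rest on an assumed positive within-subject correlation, a dose fixed within subject, and stacking.

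The direction is not guaranteed for the combined Part A and C analyses, because Cohort 15 changes SEL-110 dose after Period 1 (SAP 3.7). None of this touches the primary safety objective. It should be corrected because the intervals and p-values would otherwise be reported at levels they do not have.

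**What to change.** 1. **SAP 8.5.** Choose one. Either fit and report each period separately, or stack with a subject random intercept and a fixed period effect, and do the same for the combined Part A and C analysis. The period effect is needed because carry-over is plausible. Group-mean SEL-110 half-lives in Protocol Table 7 run from 207.6 to 299.7 h, so over a 672 h interval 2^(−672/207.6) = 0.11 to 2^(−672/299.7) = 0.21 of a terminal-phase concentration remains. Continuation also depends on Day 21 uric acid, so later periods hold a selected group.
2. **SAP 8.7.** State by-period or stacked. If stacked, add `RANDOM INTERCEPT / SUBJECT=subject_id` and period, so that the code matches the equation; if by period, drop the subject intercept from the equation. Delete the least-squares-means line in either case.
3. **Correlations (Protocol 12.5, SAP 8.5 and 9.7).** Use one row per subject, by time point or by period. If a pooled coefficient is wanted, give it with a subject-level bootstrap interval in place of the naive p-value.
4. **SAP 13.** Record any departure from the Protocol 12.5 p-values there, since it now declares no changes.

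The cost is SAP text and code, with no new data. Intervals from stacked analyses become somewhat wider.
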